In this single-blinded clinical trial, the numbers of arms were randomly assigned to six groups. The participants of the study were informed about the trial but were unaware of which treatment group they were allocated to. The clinician and researcher were aware of the groups and treatments given. All patients were allocated using Block randomization. It works by dividing participants into individual blocks and then randomly assigning treatments within each block, ensuring roughly equal numbers in each group within that block. In this clinical trial, a block size of 6 (1, 2, 3, 4, 5, 6) was employed for equal enrolment. The prepared blocks were printed in sheets and patients who met the eligibility criteria were systematically assigned in a continuous fashion. After every 6th patient, the enrolment would continue on to the next block from 1.

Arms (n=84 in each)

Arm 1: Total Etch Control group (No desensitizer application)

Arm 2: Total Etch Gluma prior to acid etchant usage

Arm 3: Total Etch Gluma desensitizer application after acid etchant usage

Arm 4: Self Etch Control group (No desensitizer application)

Arm 5: Self Etch Gluma desensitizer application prior to etching

Arm 6: Self Etch Gluma desensitizer application after self-etch adhesive usage

Materials and Methodology

Caries excavation was done using diamond burs (Mani Co., Tochigi, Japan) with water coolant. Cavity extent was until sound hard or firm discolored or non-discolored dentin was achieved. This was cross-checked by an Experienced Post Graduate Supervisor (EPGS) blinded to treatment allocation group. Those teeth with width of the cavity preparation were no more than 1/3rd of the inter-cuspal width were included. Radiographs (Durr PSP Sensor, Durr, Germany) are taken to assess the depth of the

preparation and Remaining Dentin Thickness (RDT). Two RDT measurements from mesial and distal pulp horn to floor of the preparation were calculated. Mean RDT was derived from the two readings. Radiograph assessment was done by EPGS. Teeth were excluded from the study if they had pulp exposure or a prepared cavity that did not meet standardization requirements.

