A significance level of $p < 0.05$ was considered statistically significant throughout the analysis. In the present study, the Kruskal-Wallis test was used to compare six desensitizer groups at different time intervals (Pre-operative, 24 hours, 48 hours, and 1 week post-operatively) based on Visual Analog Scale (VAS) scores. Since each time point represents a distinct clinical endpoint, a separate Kruskal-Wallis test was conducted for each, yielding **individual p-values** corresponding to each time point. As the Kruskal-Wallis test does not permit aggregation of multiple outcomes into a single p-value, **a common p-value is not statistically appropriate**.

Ranks

	Desensitizer Group	N	Mean Rank	P Value ^a
Pre Op VAS	Total etch control	86	105.48	0.003
	Total etch Gluma prior to etching	94	141.70	
	Total etch Gluma after etching	86	116.12	
	Self etch control	82	142.30	
	Self etch Gluma prior to etching	80	106.20	
	Self etch Gluma after etching	76	147.55	
	Total	504		
Post Op sensitivity 24hr VAS	Total etch control	86	125.47	0.126
	Total etch Gluma prior to etching	94	122.94	
	Total etch Gluma after etching	86	117.62	
	Self etch control	82	136.49	

	Self etch Gluma prior to etching	80	125.30	
	Self etch Gluma after etching	76	132.62	
	Total	504		
Post Op sensitivity 48hr VAS	Total etch control	86	131.74	0.050
	Total etch Gluma prior to etching	94	127.98	
	Total etch Gluma after etching	86	123.48	
	Self etch control		132.76	
	Self etch Gluma prior to etching	80	114.36	
	Self etch Gluma after etching	76	128.18	
	Total	504		
Post Op sensitivity 1 week VAS	Total etch control	86	124.24	0.013
	Total etch Gluma prior to etching	94	130.96	
	Total etch Gluma after etching	86	124.38	
	Self etch control	82	129.76	
	Self etch Gluma prior to etching	80	115.00	
	Self etch Gluma after etching	76	134.53	
	Total	504		

p < 0.05 denotes statistically significant difference. All the values exhibit non – statistically significant difference. Statistical test applied *

Kruskal – Wallis test

Ranks

	Desensitizer Group	N	Mean Rank	*P Value
Pre Op VAS	Total etch control	86	36.83	0.012
	Self etch control	82	48.45	

	Total	168		
Post Op sensitivity 24hr VAS	Total etch control	86	40.67	0.337
	Self etch control	82	44.41	
	Total	168		

p< 0.05 denotes statistically significant difference. All the values exhibit non – statistically significant difference except the pre operative pain scores. Statistical test applied * Mann Whitney U test

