DESINSENSITIZING AGENT	Pre Op VAS	Post Op VAS (24 hrs)	Post Op VAS (48 hrs)	Post Op VAS (1 week)
	Mean±SD	Mean±SD	Mean±SD	Mean±SD
Total etch control	0.86±1.67	0.37±1.05	0.37±1.05	0.21±0.77
Total etch Gluma prior to etching	1.72±2.15	0.49±1.33	0.40±1.12	0.23±0.81
Total etch Gluma after etching	1.16±2.07	0.28±0.93	0.28±0.93	0.26±0.95
Self etch control	1.88±2.25	0.66±1.32	0.41±1.00	0.12±0.33
Self etch Gluma prior to etching	0.63±1.05	0.20±0.46	0.03±0.16	0.08±0.27
Self etch Gluma after etching	2.11±2.40	0.61±1.31	0.37±0.97	0.21±0.53

- **ESTIMATION PARAMETER:** Mean Difference (Final Values)

ESTIMATED VALUE:

The mean post-operative sensitivity at 1 week was 0.18 units lower in the **Self-etch Gluma prior to etching** group compared to the **Total etch Gluma after etching** group, indicating that the former resulted in reduced sensitivity following restoration.

CONFIDENCE INTERVAL: 95%

NUMBER OF SIDES: 1 – sided

LOWER LIMIT:

Estimation Parameter: Mean Difference (Final Values)

Estimated Value: +0.18

Lower Limit (95% CI, one-sided): +0.003

Parameter Dispersion Type: Standard Deviation

Dispersion Value: 0.1077

The dispersion represents the standard deviation of the difference in mean post-operative sensitivity between the two groups.

Age limits: Patient aged between 15 to 70 years of both the gender were included

Healthy volunteers only/ with disease and why: The reason only healthy individuals are often enrolled because this helps to ensure that any observed effects are specifically related to dentin hypersensitivity and not influenced by other factors, such as an impaired immune response that could be present in individuals with certain systemic conditions.¹²

Investigator's Info:

First name: [name] **Middle name:** Nil **Last name:** [name]

Degree: MDS (Master of Dental Surgery)

[contact]

Email ID: [contact]

College Info: CSI College of Dental Sciences and Research, Madurai (CSICDSR)

(Affiliated under TN [name] University, Chennai, India)

Individual Patient sharing: Individual patient details are often not shared in this research due to concerns about privacy, confidentiality, and potential harm to participants, as well as practical and logistical challenges.¹³

References:

1. Porto I. Postoperative sensitivity on direct resin composite restorations: Clinical practice guidelines. *Indian J. Restor. Dent.* 2012; 1:1–12.

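### The only between-arm estimate compares two Gluma arms, and its claim of lower sensitivity rests on a one-sided limit read against zero with no margin

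*Combined protocol and SAP*

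**What the plan says.** After the table of means, the SAP reports one treatment-effect estimate. Under Estimated Value it states "The mean post-operative sensitivity at 1 week was 0.18 units lower in the" self-etch (SE) Gluma prior arm than in the total-etch (TE) Gluma after arm, and takes this to show that the former produced less sensitivity. The entries that follow are "NUMBER OF SIDES: 1 – sided", "Estimated Value: +0.18", "Lower Limit (95% CI, one-sided): +0.003" and "Dispersion Value: 0.1077". The last is explained: "The dispersion represents the standard deviation of the difference in mean post-operative sensitivity between the two groups". It is therefore a standard error.

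The Procedure section sets the general rule: "A significance level of $p < 0.05$ was considered statistically significant throughout the analysis". It does not say whether tests are one- or two-sided. The Type of Analysis section calls the trial a non-inferiority trial. The Procedure section says it was interpreted that way because the arms differed little from the best-performing one. No margin appears anywhere. The primary research question, in the Detailed Description, is whether Gluma reduces post-operative sensitivity.

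**The concern.** A limit of +0.003 only just excludes zero, and it does so on a one-sided interval for which no reason is given. The SAP uses it for a superiority conclusion about one pair out of 6 × 5 / 2 = 15. It does not explain the pair, which joins the smallest and largest 1-week means, and it makes no adjustment for the number of possible pairs.

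Neither arm in the pair is a control. Both received Gluma, one with the self-etch adhesive before bonding and the other with total-etch after acid. Adhesive and timing change together, so the difference cannot be attributed to either, and it says nothing about Gluma against no Gluma. A reader of the posted result would take 0.18 as the trial's treatment effect.

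**Working it through.** **Inputs.** From the SAP's table of means at 1 week: SE Gluma prior 0.08 (SD 0.27) and TE Gluma after 0.26 (SD 0.95). From the rank table: N = 80 and 86. From the Brief Summary: "Arms (n=84 in each". From the estimate block: difference 0.18, standard error 0.1077.

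**1. Reproduce the stated figures.** With 84 per arm, SE = √((0.95² + 0.27²)/84) = 0.1078, against 0.1077 stated. The limit is 0.18 − 1.645 × 0.1077 = +0.0028, which rounds to the stated +0.003. The block therefore appears to use the planned 84 per arm and a normal approximation.

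**2. The same inputs, two-sided.** 0.18 ± 1.960 × 0.1077 = −0.031 to 0.391. z = 0.18/0.1077 = 1.67, so two-sided p = 0.095 (one-sided 0.047). With the table's N of 86 and 80, a Welch interval is −0.032 to 0.392 (p = 0.095) and a pooled-variance interval is −0.037 to 0.397 (p = 0.104). The pooled one-sided limit is already −0.002.

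**3. Allowing for 15 pairs.** Bonferroni gives −0.136 to 0.496 and Tukey −0.127 to 0.487. The Bonferroni p is 15 × 0.095, capped at 1. In a normal simulation of six arms with equal true means and the printed SDs and N, the lowest-versus-highest pair passes z > 1.645 about 44% of the time.

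**4. How many units were ranked.** Weighting the 1-week mean ranks by the printed N:

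(86 × 124.24 + 94 × 130.96 + 86 × 124.38 + 82 × 129.76 + 80 × 115.00 + 76 × 134.53)/504 = 126.50

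The mean rank of N units is (N + 1)/2, so these ranks imply N = 2 × 126.50 − 1 = 252, not 504. If each arm was half its printed size (an assumption: 43 and 40), SE = √(0.95²/43 + 0.27²/40) = 0.151. The one-sided limit is then 0.18 − 1.645 × 0.151 = −0.07, and the two-sided interval is −0.12 to 0.48. On that reading even the one-sided result fails.

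**5. Sidedness of the other tests.** Kruskal-Wallis has no direction. For the 24-hour Mann-Whitney comparison of the two controls, the printed mean ranks differ by 44.41 − 40.67 = 3.74. Without ties, z = 3.74/√(N(N + 1)/12 × (1/n₁ + 1/n₂)). This is 0.498 for N = 168 and 0.702 for N = 84, with one-sided p of 0.309 and 0.241. Ties can only lower these. The reported p = 0.337 exceeds both, so by inference it is two-sided.

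**6. The contrasts that bear on the research question.** Gluma minus same-adhesive control, from the table of means. Intervals are d ± 1.96 × √(s₁²/n₁ + s₂²/n₂) with the printed N, unadjusted.

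| Contrast | Pre-op | 24 h | 48 h | 1 week |
|---|---|---|---|---|
| TE prior − TE control | +0.86 | +0.12 (−0.23 to 0.47) | +0.03 (−0.29 to 0.35) | +0.02 (−0.21 to 0.25) |
| TE after − TE control | +0.30 | −0.09 (−0.39 to 0.21) | −0.09 (−0.39 to 0.21) | +0.05 (−0.21 to 0.31) |
| SE prior − SE control | −1.25 | −0.46 (−0.76 to −0.16) | −0.38 (−0.60 to −0.16) | −0.04 (−0.13 to 0.05) |
| SE after − SE control | +0.23 | −0.05 (−0.46 to 0.36) | −0.04 (−0.35 to 0.27) | +0.09 (−0.05 to 0.23) |

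With halved N, the SE prior intervals are −0.89 to −0.03 at 24 hours and −0.69 to −0.07 at 48 hours. Those two arms began at 0.63 and 1.88, and the pre-operative Kruskal-Wallis p is 0.003.

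**The case against.** The strongest defence is the declared design. One-sided limits are usual in non-inferiority trials, and the SAP says the other protocols were judged against the best-performing arm, which explains one side of the pair. That much stands. It does not rescue the estimate: without a margin there is nothing to be non-inferior to, the limit is compared with zero, and the Procedure section derives the non-inferiority reading from the results.

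The 1-week Kruskal-Wallis p of 0.013 might also be cited. It is an omnibus rank result and does not establish this pair. The table's own footnote calls all its values non-significant.

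Four stronger readings are tempting, and the documents do not support them.

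- *Gluma looks no better, or worse, than control overall.* A reader might infer this from the 1-week contrasts, three of which favour control. At 24 and 48 hours, which are also primary time points, three of four favour Gluma.
- *The one-sided limit breaks the p < 0.05 rule.* A one-sided 95% limit is also a 0.05 rule, and the SAP never states sidedness. The inconsistency lies with the other tests, and for Mann-Whitney it is inferred.
- *The pair was hand-picked from 15.* No selection rule is documented. The pair is extreme on 1-week means, but on mean ranks the highest arm is SE Gluma after (134.53), while TE Gluma after is 124.38. The 15-pair adjustment therefore assumes a search over all pairs.
- *A two-sided interval that includes zero shows the arms are equivalent.* It does not. It reaches 0.39.

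**Conclusion.** The point holds in this form. The statement that SE Gluma prior lowered 1-week sensitivity is not supported: the two-sided 95% interval is −0.03 to 0.39 (p = 0.095), before any allowance for multiplicity. The estimate also does not address the research question, because both arms received Gluma and they differ in two respects.

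The two-sided interval rests only on the SAP's own difference and standard error. The one-sided limit of −0.07 rests on the assumption of halved arm sizes. The documents do not settle whether Gluma helps. At 1 week the relevant contrasts are small and compatible with zero. At 24 and 48 hours the differences of −0.46 and −0.38 between SE prior and SE control exclude zero unadjusted, but they cannot be separated from a pre-operative gap of 1.25 in the same direction.

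**What to change.** Delete the statement that the SE Gluma prior arm lowered sensitivity, together with the one-sided estimate that supports it. In its place report each Gluma arm against its own adhesive control: four contrasts at 24 hours, 48 hours and 1 week.

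- Adjust each contrast for the pre-operative VAS score. Unadjusted final values would carry the baseline imbalance into the comparison.
- Give two-sided 95% intervals by a method suited to skewed scores, such as a bootstrap or a rank-based estimate. The SAP itself rejects normality.
- Apply Holm adjustment to the p-values and state the family, which is 4 × 3 = 12 if all three time points count.
- State the number of restorations analysed in each arm, so that the standard errors and the printed ranks can be reconciled.

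The cost is a few lines of reanalysis on data already collected, plus rewording. The 1-week headline becomes less favourable. The direction at 24 and 48 hours after baseline adjustment cannot be known in advance.

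### The dispersion of 0.1077 is a standard error labelled as a standard deviation, and its lower limit of +0.003 falls below zero if the arm sizes implied by the mean ranks are the true ones

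*Combined protocol and SAP*

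**What the plan says.** The estimation block that closes the Statistical Analysis Plan compares 1-week sensitivity in two arms: self-etch with Gluma first, and total-etch with Gluma after the etchant. It gives "Estimated Value: +0.18", "NUMBER OF SIDES: 1 – sided" and "Lower Limit (95% CI, one-sided): +0.003". The dispersion is entered as "Parameter Dispersion Type: Standard Deviation" with "Dispersion Value: 0.1077", and a note adds: "The dispersion represents the standard deviation of the difference in mean post-operative sensitivity between the two groups". No sample size or formula is given for these figures.

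Three other places bear on them:

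- The table of means and SDs, just before the block, gives 0.26 ± 0.95 (total-etch, Gluma after) and 0.08 ± 0.27 (self-etch, Gluma first) at 1 week.
- The Brief Summary has "Arms (n=84 in each"), and the arm list in the Detailed Description repeats 84 for every arm.
- The Kruskal–Wallis rank table lists N = 86 and N = 80 for these two arms, in a total of 504. The Mann–Whitney table lists 86 and 82 for the two controls, in a total of 168.

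**The concern.** A dispersion of 0.1077 cannot be a standard deviation of scores when the two arm SDs are 0.95 and 0.27. Anyone who extracts the field as labelled, for a registry summary or a meta-analysis, would compute a standardised effect of 0.18/0.1077 = 1.67. The arm SDs give about 0.26.

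The sample size behind the figure matters too. The lower limit clears zero by only 0.003, and it stands beside a sentence crediting the self-etch, Gluma-first arm with reduced sensitivity. It is the only interval reported. If fewer independent observations lie behind the means than the tables say, the limit changes sign.

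**Working it through.** **Inputs.** SDs 0.95 and 0.27 and means 0.26 and 0.08 come from the table of means and SDs. The arm size of 84 comes from the arm lists, and 86 and 80 from the rank table. One-sided 95% confidence gives z = 1.645.

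**1. Reproduce the stated figures.** SE = sqrt(SD₁²/n₁ + SD₂²/n₂), and lower limit = 0.18 − 1.645 × SE.

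- Difference: 0.26 − 0.08 = 0.18, as stated.
- With 84 and 84: SE = sqrt((0.9025 + 0.0729)/84) = sqrt(0.011612) = 0.10776. The stated 0.1077 is this value truncated.
- Limit: 0.18 − 1.645 × 0.10776 = 0.0027, printed as +0.003.

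Both figures are recovered, so 0.1077 is a standard error.

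**2. What an SD would be.** Equal-weight pooled SD = sqrt((0.9025 + 0.0729)/2) = 0.698, and 0.18/0.698 = 0.26.

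**3. Use the tabulated 86 and 80.** SE = sqrt(0.9025/86 + 0.0729/80) = 0.1068, with limit 0.18 − 1.645 × 0.1068 = +0.0043. Allowing for rounding of the two SDs, this SE lies between 0.1061 and 0.1075. It therefore does not reach 0.1077, which supports 84 as the size used. Against 0.1077 the change is under 1%. With t quantiles the limit is +0.0033 (164 df) or +0.0027 (Welch).

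**4. Check the tabulated sizes against the ranks.** With N observations the ranks must average (N + 1)/2, ties included. For 504 that is 252.5, and for 168 it is 84.5.

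- Six arms at 1 week: (86 × 124.24 + 94 × 130.96 + 86 × 124.38 + 82 × 129.76 + 80 × 115.00 + 76 × 134.53)/504 = 63756.16/504 = 126.50. The other three time points also give 126.50. (The blank N for the self-etch control at 48 hours is taken as 82, which the total of 504 requires.)
- Implied N: 2 × 126.5 − 1 = 252.
- Two controls, pre-operative: (86 × 36.83 + 82 × 48.45)/168 = 7140.28/168 = 42.50. At 24 hours the average is also 42.50. Implied N: 2 × 42.5 − 1 = 84.
- Ranks from 504 observations that had merely been halved would average 252.5/2 = 126.25, not 126.50.

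**5. Were the arms halved evenly?** For the controls, if n₁ + n₄ = 84, the pre-operative ranks require 36.83n₁ + 48.45(84 − n₁) = 84 × 42.5 = 3570. Hence n₁ = 499.8/11.62 = 43.0 and n₄ = 41, half of 86 and 82. I also searched whole-number sizes within 7 of half the tabulated N for the controls, and within 9 for the other arms, requiring all six rank identities to hold within rounding. The only set found was 43, 47, 43, 41, 40 and 38, which is half of every tabulated N.

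**6. Recompute at 43 and 40.** SE = sqrt(0.9025/43 + 0.0729/40) = 0.1510, and 0.1510/0.1077 = 1.40. Limit: 0.18 − 1.645 × 0.1510 = −0.068.

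| Arm sizes (total-etch / self-etch) | SE | One-sided 95% lower limit |
|---|---|---|
| 84 / 84 (planned) | 0.1078 | +0.003 |
| 86 / 80 (tabulated) | 0.1068 | +0.004 |
| 43 / 40 (fits the ranks) | 0.1510 | −0.068 |

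**The case against.** The strongest reply is that the document explains itself. The standard deviation of a difference in means is its standard error, so the note under the number is right, and the arm SDs are printed nearby. That stands as far as the note goes. It does not mend the type field, which is read separately from the note and names a different quantity.

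A reader might infer that using 84 makes the interval wrong. The documents do not support that. No n is stated for the figure, so 84 is an inference, though a good one, and it is the size the arm lists give. Moving to 86 and 80 shifts the SE by about 0.001 and leaves the limit positive in the unpooled form that reproduces the plan's figures. A pooled SE (0.1102) would give 0.18 − 1.645 × 0.1102 = −0.001, but the SDs differ more than threefold and pooling is hard to defend.

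A reader might also infer that the true interval includes zero. That goes too far. No passage states arm sizes of 43 and 40, and every N printed for these two arms in the rank tables is 86 or 80. The ranks show how many observations were ranked. They do not show whether the means and SDs came from the same set, or which count is the true number of restorations. The rank discrepancy also affects every test in the plan, not this interval alone.

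**Conclusion.** The dispersion type is wrong as written: 0.1077 is the standard error of the 1-week mean difference, and read as an SD it inflates the standardised effect from about 0.26 to 1.67. This part rests only on the printed SDs and the reproduction of both stated figures.

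The apparent use of 84 in place of 86 and 80 has no practical effect.

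The effect of the rank-implied sizes is conditional but strongly supported. If the compared arms had 43 and 40 independent observations with the printed means and SDs, the SE is 40% larger than stated and the lower limit is −0.068. The documents alone cannot settle which count is right. No non-inferiority margin is given, so none of these limits can be judged against one. What is at stake is whether the interval excludes zero.

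**What to change.** - Change the dispersion type to standard error of the mean difference, and report the arm SDs (0.95 and 0.27) separately. This is a one-field edit.
- State the n and the formula behind the SE and the limit.
- Reconcile 84, 86/80 and the rank-implied 43/40 against the source dataset, establish the number of independent units per arm, and correct whichever tables are wrong.
- Recompute the SE and lower limit with those numbers. If 43 and 40 are confirmed, replace +0.003 with the recomputed limit and withdraw any statement that the interval excludes zero.

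The relabelling costs nothing. The reconciliation needs access to the data and a rerun of the tables, and the interval itself is then a few minutes' work. No new data are required.
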